## 6.7. Treatment Compliance

Patient compliance with study medication will be assessed at each visit. Compliance will be assessed by review of the Study Drug Administration Log, return of empty or unused investigational product packaging, and/or direct questioning. Deviations from the prescribed dosage regimen are to be recorded in the case report form (CRF).

Compliance is defined in Section 9.3.4.

## 6.8. Concomitant Therapy

All concomitant medication taken during the study must be recorded in the electronic CRF (eCRF). Patients will maintain their usual medication regimen throughout the study unless specifically excluded in the protocol. Patients taking permitted medications are to be on stable doses at the baseline visit (Week 0; Visit 2) through Week 16 as specified in inclusion/exclusion criteria (Sections 5.1 and 5.2). Up to Week 16, patients should not start new medications or make any changes to concomitant medications unless changes need to be made for an AE or for safety reasons. Beyond Week 16, some flexibility is allowed in concomitant medication as outlined below.

Additional drugs are to be avoided during the study unless required to treat an AE or for the treatment of an ongoing medical problem. If the need for concomitant medication arises, the investigator is to base decisions on the patient and relevant clinical factors. Any additional medication, whether prescription or over-the-counter, used at baseline (Week 0, Visit 2) and/or during the course of the study must be documented with the start and stop dates in the eCRF. Other medications may be allowed, if approved by the sponsor or its designee.

Only for patients who discontinued study treatment and have entered the Post-Study Follow-Up Period (Period 3), axSpA therapy with another agent previously excluded during the treatment period of the study may be allowed, as determined appropriate by the investigator and approved by Lilly medical.

Patients requiring surgery at any time during the study are to interrupt administration of the investigational product beginning 8 weeks prior to the surgery, or as early as possible within 8 weeks of surgery, and resume administration of the investigational product only after complete wound healing.

### *TNF alpha inhibitors:*

TNF alpha inhibitors are not to be used during any study period prior to discontinuation of investigational study medication and/or rescue ixekizumab 80 mg.

### *Vaccines:*

Live vaccines are not allowed during any of the study periods. Use of nonlive seasonal vaccinations and/or emergency vaccination (such as rabies or tetanus vaccinations) is allowed.

## 6.8.1. Concomitant Medications During Week 0 to Week 16

### *NSAIDs and Analgesics:*

NSAIDs, including COX-2 inhibitors, will be allowed up to the maximum recommended doses for pain. Patients must be on a stable dose of NSAIDs/COX-2 inhibitors for at least 2 weeks prior to baseline randomization. Introduction of a new NSAID or dose adjustment to an existing NSAID is not permitted, unless required for safety reasons (AE).

Short-acting analgesics with no anti-inflammatory action (such as paracetamol) are permitted. If administered ad hoc as needed, they are to be withheld within the 24-hour period prior to any

assessment. Aspirin (in a dose not exceeding 350 mg/day) may be taken to manage cardiovascular risk.

Opiate analgesic use is allowed but is not to exceed an average daily dose of 30 mg/day of morphine or its equivalent. Introduction of a new opiate analgesic or dose adjustment to an existing opiate analgesic is not permitted, unless required for safety reasons or as premedication for MRIs.

*Conventional DMARDs:*

Discontinuation of excluded oral or injectable cDMARDs before study enrollment must occur at least 4 weeks prior to baseline. MTX (oral or parenteral up to 25 mg/week), sulfasalazine (up to 3 g/day), or hydroxychloroquine (up to 400 mg/day) may be allowed IF at stable dose for at least 4 weeks prior to baseline randomization. These agents can only be used as single agent therapy and not in combination with other cDMARDs. If, at any time, the investigator believes that side effects or laboratory abnormalities may be attributable to the cDMARD, then cDMARD dose is to be lowered or the medication stopped. Local standard of care is to be followed for concomitant administration of folic or folinic acid if MTX is taken.

*Corticosteroids:*

*Oral corticosteroids:* If on oral corticosteroids, the dose must not exceed 10 mg/day of prednisone or its equivalent and must be stable for at least 4 weeks prior to baseline randomization. Treatment alteration in oral corticosteroid dose is not to occur prior to Week 16.

*Parenteral corticosteroids (intravenous, intramuscular, intra-articular):* Treatment with any parenteral corticosteroids is not permitted within 6 weeks prior to baseline or up to Week 16.

*Inhaled and topical steroids:* Regular use of inhaled or topical steroids will be permitted during any study period.

### **6.8.2. Concomitant Medications at or after Week 16 for Treatment Modifications (after Completion of Week 16 Assessments)**

*General:*

Changes in therapy are discouraged in the last 8 weeks prior to 52 week assessments.

*NSAIDs and Analgesics:*

Alterations of NSAIDs, including COX-2 inhibitors (dose change, introduction, or withdrawal), are allowed. Doses are recommended to be stable in the 2 weeks prior to an assessment. Any changes in frequency and/or dose must be recorded in the eCRF.

Short-acting analgesics with no anti-inflammatory action (such as paracetamol) are permitted. If administered ad hoc as needed, they are to be withheld within the 24-hour period prior to any assessment. Aspirin (dose not exceeding 350 mg/day) may be taken to manage cardiovascular risk.

Opiate analgesic use: Use of variable doses of opiate analgesics is allowed but is not to exceed an average daily dose of 30 mg morphine or its equivalent.

*Conventional DMARDs:*

Adjustment of allowed cDMARDs (eg, dose change, introduction, withdrawal of cDMARDs, or replacement of a current cDMARD with the introduction of a new cDMARD) is allowed after all assessments at Week 16 are completed. Not more than 1 adjustment of cDMARDs at 1 time within 8 weeks is recommended. cDMARD can only be used as a single agent and not in combination with other cDMARDs. Any changes must be recorded in the eCRF.

For all study periods, the maximum allowed dose is 25 mg/week for MTX, 3 g/day for sulfasalazine, and 400 mg/day for hydroxychloroquine. Local standard of care is to be followed for concomitant administration of folic or folinic acid if MTX is taken and for administration of other cDMARDs.

*Oral corticosteroids:* As of Week 16, adjustments of oral corticosteroids are allowed; however, the maximum dose is not to exceed 10 mg/day of prednisone or its equivalent at any time during these periods.

*Parenteral corticosteroids (intravenous, intramuscular, intra-articular):* As of Week 16, intra-articular injection of corticosteroid may be allowed, as needed. The joint injected must be designated along with the medication in the eCRF and must be recorded as unevaluable on the TJC/SJC assessment.

*Inhaled and topical steroids:* Regular use of inhaled or topical steroids will be permitted during any study period.

Any change in medication not addressed above is to be discussed with the clinical research physician or clinical research scientist. Patients must be instructed to consult the investigator or other appropriate study personnel at the site before taking any new medications or supplements.

## **6.9. Treatment after Study Completion**

### **6.9.1. Study Extensions**

Patients who complete this study through Visit 15 (Week 52) may be eligible to participate in a long-term study (Study RHBX) offering up to an additional 2 years of treatment, if enrollment criteria for Study RHBX are met. For patients who have completed Study RHBX through Week 52 and have exclusionary criteria for Study RHBX at Week 44 **and** Week 52, patients will complete the Post-Study Follow-Up Period (Period 3) in Study RHBX.

### **6.9.2. Continued Access**

Investigational product will not be made available to patients after conclusion of this study. However, patients who complete Study RHBX and who are eligible to continue in the long-term study (Study RHBX) may have access to investigational product for up to an additional 2 years.

## 7. Discontinuation Criteria

The reason for and date of discontinuation from study treatment (investigational product) and reason for and date of discontinuation from study participation will be collected for all randomized patients.

Patients who have taken at least 1 study dose and who discontinue study treatment prior to Week 16 or study participation (regardless of timing) are to complete an ETV and enter into post-study follow-up for at least 12 weeks after the ETV date or the last regularly scheduled visit. Patients whose ETV or last regularly scheduled visit is longer than 12 weeks after their last investigational study medication dose are not required to enter into the Post-Study Follow-Up Period. Patients who complete the study through Week 52 and who are not entering into Study RHBX are to enter into the Post-Study Follow-Up Period (Period 3) as shown in the Schedule of Activities ([Appendix 2](#)).

### 7.1. Discontinuation from Study Treatment

#### 7.1.1. *Permanent Discontinuation from Study Treatment*

The following criteria must be followed for discontinuation from study treatment.

- [1] Discontinuation of the investigational product for abnormal liver tests should be considered by the investigator when a patient meets 1 of the following conditions after consultation with the Lilly designated medical monitor:
  - ALT or AST >8 times ULN
  - ALT or AST >5 times ULN for more than 2 weeks
  - ALT or AST >3X ULN and total bilirubin level >2 times ULN or prothrombin time >1.5 times ULN
  - ALT or AST >3 times ULN with the appearance of fatigue, nausea, vomiting, right upper-quadrant pain or tenderness, fever, rash, and/or eosinophilia (>5%)
  - alkaline phosphatase >2.5 times ULN and total bilirubin >2 times ULN
  - alkaline phosphatase >2.5 times ULN with the appearance of fatigue, nausea, vomiting, right upper quadrant pain or tenderness, fever, rash, and/or eosinophilia (>5%)
- [2] Other laboratory tests (**Note:** Laboratory test(s) that may result in discontinuation based on a single result may be repeated only once if there is a technical error or clinical reason to believe a result may need to be retested. Laboratory tests can only be repeated after consultation with Lilly medical. Investigational product should not be administered in these cases until retest result is available.):

- Neutrophil (segmented) counts (see safety monitoring for neutropenia in Section 8.4.10.1):
    - $<500$  cells/ $\mu\text{L}$  ( $<0.50 \times 10^3/\mu\text{L}$  or  $<0.50$  GI/L)
    - $\geq 500$  and  $<1000$  cells/ $\mu\text{L}$  ( $\geq 0.50 \times 10^3/\mu\text{L}$  and  $<1.00 \times 10^3/\mu\text{L}$  or  $\geq 0.50$  GI/L and  $<1.00$  GI/L) (based on 2 test results; the second test performed within 1 week from knowledge of the initial result)
    - $\geq 1000$  and  $<1500$  cells/ $\mu\text{L}$  ( $\geq 1.00 \times 10^3/\mu\text{L}$  and  $<1.50 \times 10^3/\mu\text{L}$  or  $\geq 1.00$  GI/L and  $<1.50$  GI/L) (based on 3 test results as specified in Section 8.4.10.1)
      - AND - a concurrent infection
  - Total WBC count  $<2000$  cells/ $\mu\text{L}$  ( $<2.00 \times 10^3/\mu\text{L}$  or  $<2.00$  GI/L)
  - Lymphocyte count  $<500$  cells/ $\mu\text{L}$  ( $<0.50 \times 10^3/\mu\text{L}$  or  $<0.50$  GI/L)
  - Platelet count  $<50,000$  cells/ $\mu\text{L}$  ( $<50 \times 10^3/\mu\text{L}$  or  $<50$  GI/L)
- [3] The patient experiences a severe AE, an SAE, or a clinically significant change in a laboratory value that, in the opinion of the investigator, merits the discontinuation of the investigational product and appropriate measures being taken. In this case, Lilly or its designee is to be notified immediately. Refer to Adverse Events, Section 8.2.
- [4] Clinically significant systemic hypersensitivity reaction following SC administration of investigational product that does not respond to symptomatic medication or results in clinical sequelae
- [5] The patient becomes pregnant.
- [6] The patient develops a malignancy.
- Note:** Patients may be allowed to continue if they develop no more than 2 nonmelanoma skin cancers during the study.
- [7] Enrollment in any other clinical trial involving an investigational product or enrollment in any other type of medical research judged not to be scientifically or medically compatible with this study
- [8] It is recommended that the subject be assessed by a psychiatrist or appropriately trained professional to assist in deciding whether the subject is to be discontinued from the study in the following circumstances:
- The patient, at any time during the study, scores a 3 for Item 12 (Thoughts of Death or Suicide) on the QIDS-SR16;
- OR

develops active suicidal ideation with some intent to act with or without a specific plan (yes to question 4 or 5 on the “Suicidal Ideation” portion of the Columbia-Suicide Severity Rating Scale [C-SSRS]);

OR

develops suicide-related behaviors as recorded on the C-SSRS.

- [9] The investigator or attending physician decides that the patient is to be withdrawn from study treatment.
- [10] The patient requests to be withdrawn from study treatment.
- [11] Lilly or its designee stops the patient’s participation in the study or Lilly stops the study for medical, safety, regulatory, or other reasons consistent with applicable laws, regulations, and good clinical practice (GCP).
- [12] The patient becomes HBV DNA positive. The patient is to be referred to a specialist physician. Discussion of discontinuation from study treatment and from the study is provided in Section [8.4.10.2](#).

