##### **8.4.10.1. Neutropenia**

###### **8.4.10.1.1. During Treatment (Period 2)**

**During treatment with investigational product**, patients with neutrophil counts  $< 1500$  cells/ $\mu$ L ( $< 1.50 \times 10^3$ / $\mu$ L or  $< 1.50$  GI/L) are to be managed for neutropenia as follows:

- $< 500$  cells/ $\mu$ L ( $< 0.50 \times 10^3$ / $\mu$ L or  $< 0.50$  GI/L), see Discontinuation Criteria (Section [7.1](#))
- $\geq 500$  cells/ $\mu$ L and  $< 1000$  cells/ $\mu$ L ( $\geq 0.50 \times 10^3$ / $\mu$ L and  $< 1.00 \times 10^3$ / $\mu$ L or  $\geq 0.50$  GI/L and  $< 1.00$  GI/L), see Discontinuation Criteria (Section [7.1](#))
- $\geq 1000$  cells/ $\mu$ L and  $< 1500$  cells/ $\mu$ L ( $\geq 1.00 \times 10^3$ / $\mu$ L and  $< 1.50 \times 10^3$ / $\mu$ L or  $\geq 1.00$  GI/L and  $< 1.50$  GI/L), and the patient has a concurrent infection that requires systemic anti-infective therapy (for example, antibiotic, antifungal agent, antiviral agent):

- The dose of investigational product is to be withheld, the patient is to receive appropriate medical care, and a repeat test for neutrophil count is to be performed within 4 weeks from knowledge of the initial report. If the repeat neutrophil count has returned to  $\geq 1500$  cells/ $\mu\text{L}$  ( $\geq 1.50 \times 10^3/\mu\text{L}$  or  $\geq 1.50 \times 10^3/\mu\text{L}$ ) and the infection has resolved or is resolving, the patient may resume dosing of investigational product and evaluation at scheduled visits. If the neutrophil count remains  $\geq 1000$  cells/ $\mu\text{L}$  and  $< 1500$  cells/ $\mu\text{L}$  ( $\geq 1.00 \times 10^3/\mu\text{L}$  and  $< 1.50 \times 10^3/\mu\text{L}$  or  $\geq 1.00$  GI/L and  $< 1.50$  GI/L), investigational product is to continue to be withheld and a repeat neutrophil count is to again be performed within another 4 weeks. If, after 2 repeat tests, the neutrophil count still remains  $\geq 1000$  cells/ $\mu\text{L}$  and  $< 1500$  cells/ $\mu\text{L}$  ( $\geq 1.00 \times 10^3/\mu\text{L}$  and  $< 1.50 \times 10^3/\mu\text{L}$  or  $\geq 1.00$  GI/L and  $< 1.50$  GI/L), and:
  - the infection has not fully resolved; the patient will be discontinued from the study treatment.
  - the infection has resolved; the patient may resume dosing and evaluation at scheduled visits. However, if resumption of dosing is not deemed appropriate by the investigator, the patient will be discontinued from the study treatment.

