- $\geq 1000$  cells/ $\mu\text{L}$  and  $< 1500$  cells/ $\mu\text{L}$  ( $\geq 1.00 \times 10^3/\mu\text{L}$  and  $< 1.50 \times 10^3/\mu\text{L}$  or  $\geq 1.00$  GI/L and  $< 1.50$  GI/L), and the patient has no concurrent infection that requires systemic anti-infective therapy (for example, antibiotic, antifungal agent, antiviral agent):
  - Dosing may continue, and a repeat neutrophil count is to be performed 4 to 8 weeks from knowledge of the initial report. Testing may be at a regularly scheduled visit or at an unscheduled visit, as necessary.

Repeat testing is to be performed at 4- to 8-week intervals until the neutrophil count has returned to  $\geq 1500$  cells/ $\mu\text{L}$  ( $\geq 1.50 \times 10^3/\mu\text{L}$  or  $\geq 1.50$  GI/L). If the patient has 3 or more postbaseline neutrophil counts of  $\geq 1000$  cells/ $\mu\text{L}$  ( $\geq 1.00 \times 10^3/\mu\text{L}$  or  $\geq 1.00$  GI/L) and  $< 1500$  cells/ $\mu\text{L}$  ( $< 1.50 \times 10^3/\mu\text{L}$  or  $< 1.50$  GI/L), no value of  $< 1000$  cells/ $\mu\text{L}$  ( $< 1.00 \times 10^3/\mu\text{L}$  or  $< 1.00$  GI/L), and no postbaseline infection requiring systemic anti-infective therapy, the patient may continue or resume further evaluation at scheduled visits, as deemed appropriate by the investigator.

If a patient without initial concurrent infection develops an infection that requires systemic anti-infective therapy, then the patient is to be managed as indicated above for patients with concurrent infection.

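### In a patient with a treated infection, a first neutrophil count of 1000–1499 clearly stops dosing, but no clear hold is written for 500–999 while the second test is awaited

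*Protocol*

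**What the plan says.** Protocol Section 8.4.10.1.1 manages neutropenia during treatment by band.

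- **1000–1499, with infection.** Where the count is in this range "and the patient has a concurrent infection that requires systemic anti-infective therapy", the instruction is immediate: "The dose of investigational product is to be withheld, the patient is to receive appropriate medical care". The count is repeated within 4 weeks.
- **1000–1499, without such an infection.** "Dosing may continue, and a repeat neutrophil count is to be performed 4 to 8 weeks from knowledge of the initial report".
- **500–999, and below 500.** The only instruction is "see Discontinuation Criteria", pointing to Section 7.1.

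In Section 7.1.1, criterion [2], a count of 500–999 leads to discontinuation "based on 2 test results; the second test performed within 1 week from knowledge of the initial result". The neutrophil bullet refers back: "see safety monitoring for neutropenia in Section 8.4.10.1".

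Criterion [2] opens with a Note. It begins "Laboratory test(s) that may result in discontinuation based on a single result may be repeated only once", allows the repeat for a technical error or a clinical reason, requires consultation with the sponsor's medical staff first, and ends "Investigational product should not be administered in these cases until retest result is available".

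Section 6.6 (Dose Modification) refers to 8.4.10.1.1 for withholding. SAP Table RHBX.6.12, deviation D2-N, repeats the two-result rule and states no hold.

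**The concern.** The two sections refer to each other, and neither clearly says what to do with study drug between the first and second results at 500–999. For a patient with an infection under systemic treatment, the explicit hold therefore attaches to the milder count. SAP Section 6.13.4.1 grades 1000–1499 as Grade 2 and 500–999 as Grade 3.

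This looks unintended. In follow-up (Section 8.4.10.1.3) the protocol is stricter below 1000, with visits at least every 4 weeks against every 4 to 8 weeks at 1000–1499. Cytopenias (neutropenia among them) and infections are both adverse events of special interest in Section 8.2.2. At stake is whether a site that follows the text could give a further dose to an infected patient at Grade 3 while confirmation is pending.

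**Working it through.** **1. Action on a first result, band by band**

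| First count (cells/µL) | Infection needing systemic treatment | No such infection |
|---|---|---|
| <500 | Discontinue; Note's hold applies if a retest is allowed | Same |
| 500–999 | Second test within 1 week; no clear dosing instruction | Same |
| 1000–1499 | Withhold | Dosing may continue |

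The inversion appears only in the infection column. It ends with the second result, because a confirmed 500–999 is a discontinuation criterion with or without infection. A patient already on hold who falls into 500–999 is not affected: no text permits resumption at such a count.

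**2. Does the Note cover 500–999?** Its opening words describe criteria met on one result: neutrophils below 500, total white cells, lymphocytes and platelets. The second test at 500–999 is a built-in confirmation with its own one-week limit. Reading the Note to govern it would turn that confirmation into an optional retest that needs prior sponsor consultation. A broad reading is possible, but it is not clearly the written one.

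**3. Can an injection fall in the wait?**

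Inputs: injections every 2 weeks from Week 0 to Week 50 (Section 6.1); hematology before Week 50 at Weeks 4, 8, 12, 16, 20, 24, 28, 32, 36 and 44, with windows of ±2 days (Week 4), ±4 days (Weeks 8–36) and ±7 days (Week 44) (Appendix 2). Assumed: laboratory turnaround L = 1, 2 or 3 days per test, and injections kept on their nominal days.

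Take the draw as day 0 and let r (0 to 7 days) be the delay from knowing the first result to the second test. The wait runs from day L to day 2L + r, at most 2L + 7. Both end days are counted as inside.

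- *On-time draw.* That day's injection precedes the result; the next is on day 14. The wait ends by day 9, 11 or 13 for L = 1, 2 or 3. Reaching day 14 needs 2L + 7 ≥ 14, so L ≥ 3.5.
- *Draw k days early.* The draw-week injection, on day k, is inside if L ≤ k ≤ 2L + r.
- *Draw d days late.* The next injection, on day 14 − d, is inside if 14 − d ≤ 2L + r. With r = 7 this means d ≥ 7 − 2L, that is 5, 3 or 1. With r = 0 it needs d ≥ 14 − 2L = 12, 10 or 8, which no window allows.

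Window days that place an injection in the wait, for r = 7 (early + late):

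| Visit (days in window) | L = 1 | L = 2 | L = 3 |
|---|---|---|---|
| Week 4 (5) | 2 + 0 | 1 + 0 | 0 + 2 |
| Weeks 8–36 (9) | 4 + 0 | 3 + 2 | 2 + 4 |
| Week 44 (15) | 7 + 3 | 6 + 5 | 5 + 7 |

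With a same-day second test (r = 0) only early draws count: 2, 1, 0 at Week 4; 2, 3, 2 at Weeks 8–36; 2, 3, 4 at Week 44. These are counts of days, not probabilities.

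**4. Is that injection active drug?** All ten draw weeks are multiples of 4. By Table RHBX.2, before rescue, the draw-week injection (early draws) is active in both ixekizumab arms; the one two weeks later (late draws) is active only in the Q2W arm. Unscheduled draws, plausible in an infected patient, can fall on any day.

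**The case against.** The best reply is that this is a loose cross-reference and not a licence to dose. Several parts of it stand.

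- **Section 6.6 is no barrier.** A reader might infer that it forbids a hold at 500–999, because it limits dose modification and sends withholding to 8.4.10.1.1. The documents do not support that: drug may be withheld for hypertension (8.4.10.3) and is interrupted for surgery (6.8), and 6.6 lists neither. Nothing forbids a hold.
- **Judgement is available.** Criterion [3] of 7.1.1 covers a clinically significant laboratory change that merits stopping drug, with immediate sponsor notification; criterion [9] covers the investigator's decision to withdraw treatment. Both concern discontinuation; neither is a specified temporary hold.
- **The sponsor may be consulted.** The Note requires it before a repeat, but its reach to this band is as uncertain as the reach of its hold. Section 8.4.10 also asks for consultation on follow-up laboratory tests, in a paragraph that is mainly hepatic.
- **The lower band is stricter overall.** A reader might infer that the protocol treats 500–999 more leniently. It does not: confirmation is due within a week and means permanent discontinuation, whereas at 1000–1499 with infection dosing may later resume. Only the interim instruction is weaker.

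The reply does not supply a written hold for the interval.

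**Conclusion.** The point holds as a gap in a written safety instruction, limited to patients with an infection needing systemic treatment, between the first and second results at 500–999. Without such an infection there is no inversion, since dosing may also continue at 1000–1499.

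The size is small. The documents give neither the number of such patients, which is probably low, nor the laboratory turnaround. For on-time draws with a turnaround of 3 days or less, no injection is exposed. Exposure needs an early, late or unscheduled draw or a slower laboratory, and the late-draw cases also need a second test near the end of its permitted week.

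A reader might infer that sites would withhold at 1200 and dose at 700, or that about half of all waits (7 of 14 days) contain an injection. The first is conjecture about conduct. The second assumes random timing within the injection cycle, which the visit schedule does not support. Sample size, power and type I error are unaffected. It is worth correcting because the remedy is cheap and the risk is to patient safety.

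**What to change.** Add to the 500–999 bullet in 8.4.10.1.1, and mirror in 7.1.1 [2]:

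*At 500–999 cells/µL, investigational product is withheld from knowledge of the first result until the confirmatory result is available (at minimum when there is an infection needing systemic anti-infective therapy). If the second count is below 1000, discontinue per 7.1.1 [2]; if it is 1000–1499, follow the rules for that band; if it is 1500 or above and any infection has resolved or is resolving, dosing may resume.*

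This adds no visit, test or analysis. The cost is usually one delayed injection. For an early draw the longest delay is 2L + 7 − k days, leaving k + 7 − 2L days to the next dose. At Weeks 8–36:

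- L = 1 (k = 1–4): delay 8 to 5 days, gap 6 to 9.
- L = 2 (k = 2–4): delay 9 to 7 days, gap 5 to 7.
- L = 3 (k = 3–4): delay 10 or 9 days, gap 4 or 5.

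Section 6.2.1 requires injections at least 5 days apart, so only the L = 3, k = 3 case would mean a skipped injection. For late draws at the same visits the longest delay is 2L − 7 + d: at most 1 day for L = 2 and 3 days for L = 3. All these delays are shorter than the half-life of about 13 days given in Section 6.1. If the second count is 1000–1499 with infection still present, or 1500 or above with infection not resolving, the hold continues and more than one injection may be missed.
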